9.3 Rituximab/Hyaluronidase Human (For Subcutaneous Administration)

9.3.1. Description

Rituximab/hyaluronidase human (Rituxan Hycela®) is a genetically engineered chimeric murine/human monoclonal IgG1 kappa antibody directed against the CD20 antigen found on pre-B and mature B cells. In this formulation, it is combined with hyaluronidase human, an endoglycosidase (Genentech 2018). Rituximab is produced by mammalian Chinese hamster ovary cells. The protein has an approximate molecular weight of 145 kD. Hyaluronidase human increases permeability of the subcutaneous tissue by temporarily depolymerizing hyaluronan.

The drug is provided as a colorless to yellowish, clear to opalescent, preservative-free liquid solution. Each mL of solution contains rituximab (120 mg), hyaluronidase human (2,000 Units),

Version 9, 18 Feb 2020

L-histidine (0.53 mg), L-histidine hydrochloride monohydrate (3.47 mg), L-methionine (1.49 mg), polysorbate 80 (0.6 mg), α,α-trehalose dihydrate (79.45 mg), and Water for Injection.

9.3.2 Packaging

For use in patients with FL/DLBCL, rituximab/hyaluronidase human is supplied in single-dose vials containing 1,400 mg rituximab and 23,400 Units hyaluronidase human per 11.7 mL of solution.

9.3.3 Source

Unless otherwise instructed by the sponsor, the rituximab/hyaluronidase human to be used in this study may be obtained from available commercial supplies.

9.3.4. Storage and Stability

Rituximab/hyaluronidase human vials are stable at 2°C-8°C (36°F-46°F). Vials should be protected from direct sunlight and should not be frozen or shaken.

Diluted rituximab/hyaluronidase human solutions for injection may be stored at 2°C-8°C (36°F-46°F) for 48 hours and are known to be stable for an additional 8 hours at room temperatures up to 30°C (86°F) in diffuse light. However, since rituximab solutions do not contain a preservative, solutions should be used as soon as possible after withdrawal from the vial.

Rituximab/hyaluronidase is compatible with polypropylene and polycarbonate syringe material and stainless-steel transfer and injection needles.

9.3.5 Preparation

Before use, the rituximab/hyaluronidase human vials should be inspected for particulate matter or discoloration. Any vial with evidence of particulates or discoloration should not be used.

Using aseptic technique, the entire 11.7 mL of rituximab/hyaluronidase human should be withdrawn from the vial via a hypodermic needle into a syringe and the vial should be discarded.

9.3.6 Accountability

Acquisition, storage, control, and disposal of rituximab/hyaluronidase used in the study should be performed according to institutional procedures and policies.

The investigator and/or the responsible site personnel must maintain accurate records of the source, dates of administration, quantities of administration, and lot numbers of the rituximab/hyaluronidase dispensed for this study.

Section 10. Pregnancy

Changes: Information regarding pharmacovigilance reporting of pregnancies was corrected.

Pregnancy occurring in a subject is not considered an AE. However, the investigator must capture pregnancy information for subject and/or subject's partner (as applicable) on a pregnancy report form within 24 hours of learning of the pregnancy. Then the site

• Completes the pregnancy form with as much information as possible; however, at a minimum the Subject identification number, name of product, and name of reporter is required;

Version 9, 18 Feb 2020

Signs Pregnancy Notification form; and

Subjects determined to be pregnant must be immediately removed from treatment and will be followed by the investigator until termination of the pregnancy or delivery of the child. Additional information on the course of the pregnancy should be supplied on follow-up forms as it becomes available and at minimum at termination or birth.

Section 12. Pharmacokinetic Assessments

Changes: (Paragraph 3 only): Reference to the laboratory manual was included.

Comprehensive information on blood sample acquisition, handling, storage and sample shipments can be found in the laboratory manual "Procedures for Processing and Shipping PK and Biomarker Samples." pharmacokinetic laboratory manual.

Section 13. Biomarker Assessments

Changes: Information regarding biopsy procedures was clarified. Reference to the laboratory manual was included.

For subjects with NHL, archival tissue from the most recent available biopsy or surgery or fresh tumor tissue (preferred) or archival tissue from the most recent available biopsy or surgery (within 4 months prior to the start of screening) must be obtained pretreatment. For subjects undergoing a biopsy, adequate tumor tissue should be acquired via excisional biopsy, incisional biopsy or core needle biopsy (e.g., > 3 passes using a 16-gauge core needle). Confirmation of tumor in biopsy with fine needle aspirate, touch prep, or FFPE processing is requested when possible. The tumor lesion selected should not have been previously irradiated and should not be an index lesion that is followed for response assessment. Alternatively, cells from a bone marrow aspirate may be obtained in subjects with bone marrow involvement due to NHL (>50% NHL cells). For subjects undergoing a biopsy, adequate tumor tissue should be acquired via excisional biopsy, incisional biopsy or core needle biopsy (e.g., ≥ 3 passes using a 16 gauge core needle). Tissue will be submitted for evaluation of the percentage of tumor cells and analysis of genetic alterations and/or gene expression that may predict anti-lymphoma activity and/or pharmacodynamics activity. In addition, tumor may be evaluated for known prognostic characteristics (e.g., for DLBCL: ABC or GCB subtype; expression of BCL2, BCL6, Ki-67, CD20, and MYC; other mutational status), for PDL1 status, and for immune infiltration.

Comprehensive information on tissue acquisition, handling, storage and sample shipments can be found in the laboratory manual "Procedures for Processing and Shipping PK and Biomarker Samples." biomarker sample process documents.

Section 14.1.2. Stage 2 (Cohort Expansion)

Changes: A statistical justification for accrual of additional patients with FL to receive LAM-002A monotherapy or LAM-002A/rituximab was included.

As indicated in Section 6.1.2, expansion cohorts of 6 subjects will be accrued. Enrollment of 6 subjects per cohort offers the opportunity to determine if there is any antitumor activity sufficient to warrant further development in the selected tumor types. An ORR of \geq 35% is considered of potential interest in each of the selected indications. If 0/6 subjects in a cohort

Clinical Study Report 16.1 Study Information Protocol: LAM-002A-NHL-CLN01

Version 9, 18 Feb 2020

experience an objective response, then a population ORR of \geq 35% for that cancer can be excluded with > 90% certainty (1-sided exact binomial 90% CI upper bound = 32%).

Based on the observation of objective responses among study subjects with FL receiving either LAM-002A monotherapy or LAM-002A/rituximab, expanded accrual of subjects with relapsed FL is planned to evaluate the level of activity with these 2 regimens. Preference will be given to enrolling subjects to receive LAM-002A monotherapy before enrolling subjects to receive LAM-002A/rituximab.

Based on historical data with other treatments (Zelenetz 2014), it is known that an ORR of \leq 20% in subjects with relapsed FL receiving LAM-002A monotherapy would be uninteresting while achieving a target ORR of \geq 40% would suggest that further development is warranted. Sequential boundaries will be used to continuously monitor that the ORR is \geq 40% while excluding an ORR of \leq 20% using a 1-sided test with a significance level of 0.05. A significant result with this testing would conclude with 95% confidence that the actual ORR is \geq 20%. Accrual of up to \sim 20 evaluable subjects will be considered with the potential to stop accrual early if the boundary is crossed. Thus, accrual can be considered sufficient if the following n/N values are observed: 4/5, 4/6, 4/7, 5/8, 5/9, 5/10, 5/11, 6/11, 6/12, 6/13, 6/14, 7/15, 7/16, 7/17, 8/18, 8/19, 8/20. For all these values, the ORR is \geq 40% with a lower 1-sided binomial confidence bound of \geq 20%.

As noted above, the target ORR with LAM-002A alone is ~40%. Adding rituximab or rituximab hyaluronidase human to LAM-002A would be expected to enhance the ORR over that associated with single-agent LAM-002A. Thus, the combination of LAM-002A/rituximab could warrant further development if an ORR of \geq 60% could be targeted in preference to an ORR of < 40%. Accordingly, for combination therapy, sequential boundaries will be used to continuously monitor that the ORR is \geq 60% while excluding an ORR of 39% using a 1-sided test with a significance level of 0.05. A significant result with this testing would conclude with 95% confidence that the actual ORR is \geq 39%. Accrual of up to \sim 20 evaluable subjects will be considered with the potential to stop accrual early if the boundary is crossed. Thus, accrual can be considered sufficient if the following n/N values are observed: 7/10, 8/11, 8/12, 9/13, 9/14, 10/15, 10/16, 11/17, 11/18, 12/19, 12/20. For all these values, the ORR is \geq 60% with a lower 1-sided binomial confidence bound of \geq 39%.

Experience indicates the rates of discontinuations from rituximab or atezolizumab therapy are < 5% (Genentech 2016, Genentech 2017). A rate of AE discontinuations of therapy due to adverse events of \geq 25% in the 2 combination therapy groups of LAM-002A/rituximab (N = 12) or LAM-002A/atezolizumab (N = 12) would suggest a potential adverse interaction among the components of the combination therapy. Sequential Pocock-type boundaries will be used to continuously monitor the rate of AE discontinuations and to test the null hypothesis, after each subject, that the event rate is \geq 0.25 using a 1-sided significance test of \sim 0.05. AE discontinuation rates will be considered excessive if the following n/N values are observed: -/1, -/2, 3/3, 3/4, 4/5, 4/6, 5/7, 5/8, 5/9, 6/10, 6/11, 7/12. With this method, the probability of detecting an AE discontinuation safety signal ranges from 0.091 to \geq 0.820 for true discontinuation rates of 25% to \geq 60%. If excessive levels of AE discontinuation are observed, the sponsor, working in collaboration with the cooperating companies and investigators, will take appropriate actions (eg, continuation of the cohort with modifications in design or monitoring plan, interruption of cohort accrual, cohort therapy discontinuation).

Version 9, 18 Feb 2020

Section 22. List of References

Changes: Information regarding drugs with known risk of QT prolongation or torsades de pointes was updated and the relevant reference was revised accordingly. Use of either intravenously administered rituximab or subcutaneously administered rituximab hyaluronidase human was permitted; accordingly, reference was made to rituximab hyaluronidase human prescribing information.

CredibleMeds. [homepage on the Internet]. Arizona: Combined list of drugs that prolong QC and/or cause tosrades de pointes (TDP). [Updated 2014 May 32; Cited 2015 June 12]. Available from: Woosley RL, Romero KA. Drugs with known risk of torsades de pointes. 2018 Oct 31. Available at: https://www.crediblemeds.org (accessed 2018 Dec 17).

Genentech. Rituxan Hycela® (rituximab and hyaluronidase human) prescribing information. 2018 Apr. Avaliable at: https://www.gene.com/download/pdf/rituxan hycela prescribing.pdf (acessed 2018 Dec 18).

Appendix 3. Potential Drug Interactions with LAM-002A, Table 16 Drugs Known to Prolong the QT Interval and/or Cause Torsades De Pointes (TDP)

Changes: Information regarding drugs with known risk of QT prolongation or torsades de pointes was updated. To avoid formatting problems, the former table was removed without displaying it in strikeout font.

Table 16: Drugs Known to Prolong the QT Interval and/or Cause Torsades De Pointes (TDP)

Generic Name	Brand Names (Partial List)	Drug Class	Therapeutic Use
Amiodarone	Cordarone®, Pacerone®, Nexterone®	Antiarrhythmic	Abnormal heart rhythm
Anagrelide	Agrylin®, Xagrid®	Phosphodiesterase 3 inhibitor	Thrombocythemia
Arsenic trioxide	Trisenox®	Anticancer	Cancer (leukemia)
Astemizole (removed from market)	Hismanal®	Antihistamine	Allergic rhinitis
Azithromycin	Zithromax®, Zmax®	Antibiotic	Bacterial infection
Bepridil (removed from market)	Vascor®	Antianginal	Angina Pectoris (heart pain)
Chloroquine	Aralen®	Antimalarial	Malaria
Chlorpromazine	Thorazine®, Largactil®, Megaphen®	Antipsychotic / Antiemetic	Schizophrenia, nausea, many others
Cilostazol	Pletal®	Phosphodiesterase 3 inhibitor	Intermittent claudication
Ciprofloxacin	Cipro®, Cipro-XR®, Neofloxin®	Antibiotic	Bacterial infection
Cisapride (removed from market)	Propulsid®	Gastrointestinal stimulant	Increase gastrointestinal motility
Citalopram	Celexa®, Cipramil®	Antidepressant, selective serotonin reuptake inhibitor	Depression

Version 9, 18 Feb 2020

Generic Name	Brand Names (Partial List)	Drug Class	Therapeutic Use
Clarithromycin	Biaxin®, Prevpac®	Antibiotic	Bacterial infection
Cocaine	Cocaine	Local anesthetic	Anesthesia (topical)
Disopyramide	Norpace®	Antiarrhythmic	Abnormal heart rhythm
Dofetilide	Tikosyn®	Antiarrhythmic	Abnormal heart rhythm
Domperidone (only on non-US market)	Motilium®, Motillium®, Motinorm Costi®, Nomit®	Antinausea	Nausea, vomiting
Donepezil	Aricept®	Cholinesterase inhibitor	Dementia (Alzheimer's Disease)
Dronedarone	Multaq®	Antiarrhythmic	Abnormal heart rhythm
Droperidol	Inapsine®, Droleptan®, Dridol®, Xomolix®	Antipsychotic / Antiemetic	Anesthesia (adjunct), nausea
Erythromycin	E.E.S.®, Robimycin®, EMycin®, Erymax®, Ery- Tab®, Eryc Ranbaxy®, Erypar®, Eryped®, Erythrocin Stearate Filmtab®, Erythrocot®, E-Base®, Erythroped®, Ilosone®, MY-E®, Pediamycin®, Zineryt®, Abboticin®, Abboticin- ES®, Erycin®, PCE Dispertab®, Stiemycine®, Acnasol®, Tiloryth®	Antibiotic	Bacterial infection, increase gastrointestinal motility
Escitalopram	Cipralex®, Lexapro®, Nexito®, Anxiset-E® (India), Exodus® (Brazil), Esto® (Israel), Seroplex®, Elicea®, Lexamil®, Lexam®, Entact® (Greece), Losita® (Bangladesh), Reposil® (Chile), Animaxen® (Colombia), Esitalo® (Australia), Lexamil® (South Africa)	Antidepressant, selective serotonin reuptake inhibitor	Depression (major), anxiety disorders
Flecainide	Tambocor®, Almarytm®, Apocard®, Ecrinal®, Flécaine®	Antiarrhythmic	Abnormal heart rhythm
Fluconazole	Diflucan® , Trican®	Antifungal	Fungal infection
Gatifloxacin (removed from market)	Tequin®	Antibiotic	Bacterial infection
Grepafloxacin	Raxar®	Antibiotic	Bacterial infection
Halofantrine	Halfan®	Antimalarial	Malaria
Haloperidol	Haldol® (US & UK), Aloperidin®, Bioperidolo®, Brotopon®,	Antipsychotic	Schizophrenia, agitation

Version 9, 18 Feb 2020

	Brand Names (Partial		
Generic Name	List)	Drug Class	Therapeutic Use
	Dozic®, Duraperidol® (Germany), Einalon S®, Eukystol®, Halosten®, Keselan®, Linton®, Peluces®, Serenace®, Serenase®, Sigaperidol®		
Ibogaine (only on non-US market)	None	Psychedelic	Narcotic addiction, unproven
Ibutilide	Corvert®	Antiarrhythmic	Abnormal heart rhythm
Levofloxacin	Levaquin®, Tavanic®	Antibiotic	Bacterial infection
Levomepromazine (methotrimeprazine) only on non-US market)	Nosinan®, Nozinan®, Levoprome®	Antipsychotic	Schizophrenia
Levosulpiride (only on non-US market)	Lesuride®, Levazeo®. Enliva® (with rabeprazole)	Antipsychotic	Schizophrenia
Levomethadyl acetate (removed from market)	Orlaam®	Opioid agonist	Narcotic dependence
Mesoridazine (removed from market)	Serentil®	Antipsychotic	Schizophrenia
Methadone	Dolophine®, Symoron®, Amidone®, Methadose®, Physeptone®, Heptadon®	Opioid agonist	Narcotic dependence, pain
Moxifloxacin	Avelon® Avelon®	Antibiotic	Bacterial infection
Ondansetron	Zofran®, Anset®, Ondemet®, Zuplenz®, Emetron®, Ondavell®, Emeset®, Ondisolv®, Setronax®	Antiemetic	Nausea, vomiting
Oxaliplatin	Eloxatin®	Antineoplastic Agent	Cancer
Papaverine HCl	none	Vasodilator, Coronary	Diagnostic adjunct
Pentamidine	Pentam®	Antifungal	Fungal infection (Pneumocystis pneumonia)
Pimozide	Orap®	Antipsychotic	Tourette's Disorder
Probucol (removed from market)	Lorelco®	Antilipemic	Hypercholesterolemia
Procainamide	Pronestyl®, Procan®	Antiarrhythmic	Abnormal heart rhythm
Propofol	Diprivan®, Propoven®	Anesthetic, general	Anesthesia
Quinidine	Quinaglute®, Duraquin®, Quinact®, Quinidex®, Cin-Quin®, Quinora®	Antiarrhythmic	Abnormal heart rhythm
Roxithromycin (only on non-US market)	Rulide®, Xthrocin®, Roxl-150®, Roxo®, Surlid®, Rulide®,	Antibiotic	Bacterial infection

Version 9, 18 Feb 2020

Generic Name	Brand Names (Partial List)	Drug Class	Therapeutic Use
	Biaxsig®, Roxar®, Roximycinv®, Roxomycin®, Rulid®, Tirabicin®, Coroxin®		
Sevoflurane	Ulane®, Sojourn®	Anesthetic, general	Anesthesia
Sotalol	Betapace®, Sotalex®, Sotacor®	Antiarrhythmic	Abnormal heart rhythm
Sparfloxacin (removed from market)	Zagam®	Antibiotic	Bacterial infection
Sulpiride (only on non-US market)	Dogmatil®, Dolmatil®, Eglonyl®, Espiride®, Modal®, Sulpor®	Antipsychotic, atypical	Schizophrenia
Sultopride (only on non-US market)	Barnetil®, Barnotil®, Topral®	Antipsychotic, atypical	Schizophrenia
Terfenadine (removed from market)	Seldane®	Antihistamine	Allergic rhinitis
Terlipressin (only on non-US market)	Teripress®, Glypressin®, Terlipin®, Remestyp®, Tresil®, Teriss®, and others	Vasoconstrictor	Septic shock

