Subjects will be allocated to the cohorts by the study sponsor working in collaboration with each investigator considering the availability of openings for enrollment in Stage 1 or 2, disease type (i.e., FL, MZL, DLBCL-GCB, DLBCL-ABC, or other indications), therapy history (e.g., prior use of anti-CD20 or anti-PD1/PDL1 antibodies), and current disease status (e.g., potential to benefit from rituximab treatment based on past responses to anti-CD20 antibody therapy).

During Stage 1 dose ranging with LAM-002A monotherapy, allocation will be performed according to a 3+3 dose-escalation procedure with the requirement that each cohort of 3 subjects be observed for \geq 4 weeks before another cohort is enrolled (as detailed in Section 6.6). During Stage 2 cohort expansion evaluating LAM-002A monotherapy, allocation will be performed as subjects present to the accruing clinics and there will be no specific restrictions on the cadence of enrollment. During Stage 2 cohort-expansion of LAM-002A combinations with rituximab and atezolizumab, enrollment of the first 3 subjects in each combination cohort will be restricted such that each subject must be enrolled sequentially and observed for \geq 3 weeks before the next subject is enrolled. Beginning with the 4th patient in each combination group, further enrollment may proceed without restriction as long as the continuous reassessment boundaries for toxic drug discontinuations are not met (as detailed in Section 6.8.2.5 and Section 6.12).

Version 9, 18 Feb 2020

Section 6.1.4 Subject Evaluability

Change: This section was added to clarify subject evaluability for the dose-ranging and cohort-expansion portions of the study.

A Stage 1 subject will be considered evaluable if the subject meets the definition for evaluability of Cycle 1 DLT as described in Section 6.6. A Stage 2 subject will be considered evaluable if the subject has both baseline and ≥ 1 on-study tumor assessments sufficient to allow a determination of response to study therapy.

Section 6.2. Number of Subjects

Change: The number of subjects was updated to reflect the new dose-escalation and cohort-expansion plans.

As many as 110 Approximately 115 evaluable subjects (evaluable subjects include those who complete Cycle 1 dosing [administered at least 75% of doses] and have sufficient safety data, or who are withdrawn from the study due to a DLT in Cycle 1) will be enrolled, assuming that:

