Change: The protocol was modified to permit evaluation of single-agent LAM-002A or the LAM-002A/rituximab combination in additional patients with FL. Use of either intravenously administered rituximab or subcutaneously administered rituximab hyaluronidase human was permitted.

Once the MTD and/or recommended phase 2 dose (RP2D) and schedule is determined, the study will enter the expansion stage, in which cohorts of subjects will be accrued in order to obtain additional information on safety, tolerability, preliminary anti-tumor activity, PK, and pharmacodynamic data at the RP2D and schedule when LAM-002A is administered alone or in combination with rituximab/rituximab hyaluronidase or atezolizumab. Expansion-stage cohorts will comprise groups of subjects with specific types of previously treated, relapsed, progressive, and measurable NHL who will receive LAM-002A monotherapy or LAM-002A-containing combination therapy as shown in Table 2. For both monotherapy and combination cohorts, the starting dose of LAM-002A will be 125 mg BID administered continuously.

Version 9, 18 Feb 2020

Table 2: Expansion Stage Disease Types and Therapies

Cohort Number	NHL Type	Investigational Drug	Combination Drug	Evaluable Subjects, n
1	FL	LAM-002A		6 Up to ~20
2	MZL	LAM-002A		6
3	DLBCL-GCB	LAM-002A		6
4	DLBCL-ABC	LAM-002A		6
5	FL or MZL	LAM-002A	Rituximab or rituximab hyaluronidase human	6 Up to ~20 with FL
6	DLBCL-GCB or DLBCL-ABC	LAM-002A	Rituximab or rituximab hyaluronidase human	6
7	FL or MZL	LAM-002A	Atezolizumab	6
8	DLBCL-GCB or DLBCL-ABC	LAM-002A	Atezolizumab	6

Abbreviations: ABC: activated B-cell (subtype); DLBCL: diffuse large B-cell lymphoma; FL: follicular lymphoma; GCB: germinal center B-cell (subtype); MZL: marginal zone lymphoma; NHL: non-Hodgkin lymphoma

Section 6.2 Number of Subjects

Change: Information regarding the total potential accrual to the study was updated consistent with modifications to the protocol to evaluate single-agent LAM-002A or the LAM-002A/rituximab combination in additional patients with FL.

As many as $\underline{145}$ $\underline{110}$ subjects will be enrolled, assuming that:

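### Section 14.1.2: no responses in six subjects excludes an ORR of 35% for a cancer only if all six have it; in mixed cohorts 6, 7 and 8 it bounds only the average of the enrolled mix

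*Combined protocol and SAP*

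**What the plan says.** Section 14.1.2 (Stage 2, Cohort Expansion) gives the reason for the cohort size: "Enrollment of 6 subjects per cohort offers the opportunity to determine if there is any antitumor activity". It adds that an ORR of 35% or more "is considered of potential interest in each of the selected indications". If 0/6 respond, a population ORR at that level "for that cancer can be excluded with > 90% certainty (1-sided exact binomial 90% CI upper bound = 32"%). The sentence is worded for a cohort in general and makes no exception.

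Table 2 in Section 6.1.2 gives monotherapy cohorts 1 to 4 one type each: FL, MZL, DLBCL-GCB and DLBCL-ABC. Three combination cohorts of six subjects take two types. Cohorts 6 and 8 are labelled "DLBCL-GCB or DLBCL-ABC", and cohort 7 admits FL or MZL. Section 6.1.3 allocates subjects by, among other things, "disease type (i.e., FL, MZL, DLBCL-GCB, DLBCL-ABC, or other indications"). The text available sets no minimum number per type within a mixed cohort.

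For FL, Section 14.1.2 now says that "expanded accrual of subjects with relapsed FL is planned to evaluate the level of activity with these 2 regimens". FL monotherapy and FL with rituximab (cohort 5) may each accrue up to about 20 evaluable subjects, with their own response boundaries.

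**The concern.** The calculation treats the cohort as six subjects who share one ORR, and the conclusion is stated for one cancer. Cohorts 1 to 4 have that structure. Cohorts 6, 7 and 8 need not: a type may contribute anything from none to all six of the subjects. The plan itself separates these types, since each has its own monotherapy cohort and the allocation rule lists them individually.

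At stake is what the study report may say. Under the present wording, 0/6 in a mixed cohort could be reported as excluding a 35% ORR for a type represented by one to three subjects, with a stated certainty that its own data do not give.

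**Working it through.** **Inputs.** Cohort size 6, ORR of interest 35% and 1-sided confidence 90% (Section 14.1.2); cohort composition (Table 2). Two quantities are not stated and are treated as assumptions: the number *m* of the six subjects who have the type of interest (1 to 5), and the ORR *q* of the other type (0% to 35%).

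**Step 1: the plan's own figures.** With 0 responses in *n* subjects, the exact 1-sided 90% upper bound is 1 − 0.10^(1/n). For n = 6 this is 31.9%, which the plan gives as 32%. If all six have ORR 35%, P(0/6) = 0.65^6 = 7.5%, so the certainty is 92.5%. Both statements reproduce for six subjects with one common ORR.

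**Step 2: what 0/6 bounds in a mixed cohort.** P(0/6) = 0.65^m × (1 − q)^(6 − m) when one type has ORR 35%. For any pair of ORRs and a fixed split, the corresponding product is at most (1 − average ORR)^6, because a geometric mean cannot exceed the arithmetic mean. The 32% bound therefore holds, conservatively, for the average ORR of the enrolled mix. Example: a 3:3 split with ORRs of 70% and 0% averages 35%, and P(0/6) = 0.30^3 = 2.7%, below 7.5%.

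**Step 3: what it bounds for one type.** Only that type's own *m* subjects carry information on its ORR. The bound is 1 − 0.10^(1/m), and the certainty of excluding 35% is 1 − 0.65^m.

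| m | Upper bound for 0/m | Certainty of excluding 35% |
|---|---|---|
| 1 | 90.0% | 35% |
| 2 | 68.4% | 58% |
| 3 | 53.6% | 73% |
| 4 | 43.8% | 82% |
| 5 | 36.9% | 88% |
| 6 | 31.9% | 92.5% |

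Only m = 6 brings the bound below 35%. In any true split both types have m of 5 or less, so 35% is excluded for neither. This step needs no assumption about *q*.

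**Step 4: how often a type with true ORR 35% falls in a 0/6 cohort.** From 0.65^m × (1 − q)^(6 − m):

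| Split (m : 6 − m) | q = 0% | 10% | 20% | 30% | 35% |
|---|---|---|---|---|---|
| 1:5 | 65.0% | 38.4% | 21.3% | 10.9% | 7.5% |
| 2:4 | 42.3% | 27.7% | 17.3% | 10.1% | 7.5% |
| 3:3 | 27.5% | 20.0% | 14.1% | 9.4% | 7.5% |
| 4:2 | 17.9% | 14.5% | 11.4% | 8.7% | 7.5% |
| 5:1 | 11.6% | 10.4% | 9.3% | 8.1% | 7.5% |

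The comparison is 7.5% for a single-type cohort. At 3:3 the probability passes 10% only if *q* is below about 29%.

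**The case against.** Several points on the other side stand.

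- **The bound is not wrong for the cohort.** A reader might infer that in a mixed cohort 0/6 tests whether both types reach 35%, or that the 32% figure is invalid there. Step 2 shows otherwise: it is a valid and conservative bound on the mix. The fault is in attaching it to a single cancer.
- **For cohorts 6 and 8 the cancer could be DLBCL.** Inclusion criteria 2 and 3 name DLBCL as one diagnosis, and the Table 2 abbreviations call GCB and ABC subtypes. On that reading the sentence can stand for DLBCL as enrolled. Against it, Section 6.1.3 lists the two as disease types and cohorts 3 and 4 study them separately, so the text is ambiguous. Cohort 7 has no such reading: FL and MZL are separate entries in inclusion criterion 2.
- **Nothing is dropped by rule.** A reader might infer that a type with 35% ORR would be abandoned after 0/6. The text available attaches no futility stop or development decision to that result, and each type also has its own monotherapy cohort.
- **The largest probabilities sit at the unfavourable end.** The 65% needs one subject of the active type and no activity in the other five. For cohort 7, an ORR of 0% in FL fits poorly with the FL responses that Section 14.1.2 reports for LAM-002A alone and with rituximab.
- **Cohort 5 is not a live case for FL**, because it now has its own boundaries.

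The Stage 2 text was read from the amendment log; the preceding body of the protocol was not available. A minimum per type, or reporting by type, might be specified there.

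**Conclusion.** The point holds in a limited form. The per-cancer exclusion in Section 14.1.2 is correct for six evaluable subjects of one type. It is not correct per type in cohort 7, nor in cohorts 6 and 8 unless the cancer meant is DLBCL overall. The firm result is Step 3: under any split the type-specific upper bound is at least 37%, so 35% is excluded for neither type.

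The probabilities in Step 4 are conditional on a split and an other-type ORR that the documents do not give. A reader might infer that the error is always far above 10%. It is not: it stays at 7.5% if both types have ORR 35%, and at 3:3 it runs from 27.5% down to that value. The consequence is for interpretation and reporting in an exploratory expansion stage.

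**What to change.** In Section 14.1.2:

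1. Limit the sentence on excluding 35% for a cancer with more than 90% certainty to cohorts with six evaluable subjects of one type.
2. State that in cohorts 6, 7 and 8 a result of 0/6 bounds only the ORR of the enrolled mix.
3. Report responses and the exact 1-sided 90% upper bound by type, each on that type's own number of subjects.
4. Claim exclusion of 35% for a type only if its own bound is below 35%.

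The cost is a change of wording and one table by type. Histology is collected at screening (Section 8.1.3), and tumour tissue is to be evaluated for ABC or GCB subtype (Section 8.1.5). Enrolment and sample size do not change. The downside is that the mixed cohorts can no longer claim exclusion for each type, and the bounds by type will be wide: 54% for 0/3, for example.
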